### **1. KEY ROLES:**

The NIH/NIMH-funded research study is to be conducted by Johns Hopkins University School of Public Health (JHU) and TB HIV Care (THC) in South Africa. TB HIV Care will lead the data collection in the provinces of KwaZulu-Natal, Mpumalanga, Eastern Cape and North West Province, South Africa. TB HIV Care has extensive experience working with female sex workers (FSW) and adolescent girls and young women (AGYW) through service delivery programmes funded by the Centers for Disease Control (CDC) and the Global Fund to Fight AIDS, Tuberculosis and Malaria.

Human subjects research oversight and approvals will be provided by the Faculty of Health Sciences Research Ethics Committee at the University of Pretoria and the Johns Hopkins School of Public Health Institutional Review Board. All investigators and study staff involved with the data collection and analysis will be trained in the protection of human subjects in research and good clinical practice. Interviewers will receive training on the questionnaire, interviewing techniques, and working with FSW and AGYW.

The principal investigators (PIs) and Co-Investigators will make regular site visits during implementation to provide training, review study progress, support ongoing research activities, and provide technical assistance. The Project Coordinator employed by TB HIV Care will ensure that the study team follows the protocol and that all data collection materials and forms are completed and stored in accordance with the protocol and standard operating procedures. These activities will be monitored by the local PI, JHU PI, and other investigators on site visits.

### **2. BACKGROUND AND RATIONALE:**

The HIV epidemic in South Africa is characterized by extremely high HIV incidence rates among marginalized adolescent girls and young women (AGYW) aged 15-24 and female sex workers (FSW). Given intersections of biological, behavioral, and structural risks, high HIV incidence has been sustained despite HIV testing and condom promotion programmes. Pre-exposure prophylaxis (PrEP), currently formulated as a once daily pill taken to prevent HIV acquisition, represents an HIV prevention tool with great promise to finally achieve an AIDS-Free generation in the country most burdened by HIV. While PrEP has been effective at preventing HIV among women with high perceived HIV risk in supportive partnerships (e.g., disclosed, HIV serodifferent couples), limited uptake and early discontinuation has limited the HIV prevention effectiveness for marginalized, young women. Although AGYW and FSW are often perceived as separate groups, data from across Southern and Eastern Africa reinforce overlapping vulnerabilities - with over two times the odds of HIV infection among AGYW engaged in transactional sex compared to other AGYW. Moreover, young FSW have often not yet developed sufficient health literacy and self-efficacy to protect themselves from occupational HIV exposure. In general, adolescence and early adulthood are times of transition and often volatility, amplifying the risks young women experience. Biological, economic and structural factors, including social norms reinforcing gender inequalities and violence, heighten vulnerabilities to HIV acquisition among marginalized young women.

PrEP has been prioritized by the South African government, yet evidence of how to implement PrEP scale-up and promote both uptake and adherence for marginalized, young women is lacking. Restricted promotion of PrEP outside of population-specific (e.g. either sex workers or men who have sex with men) programming has resulted in low PrEP awareness at the community level, and thus those considering PrEP often experience negative social influence from friends, partners, family and even health care providers about PrEP use. Furthermore, among those taking up PrEP, persistence among women halves by 1 month and continues a sharp decline during the first 3-6 months; effective strategies to target uptake and persistence during these critical periods are needed. Several barriers to PrEP adherence have been identified, ranging from individual level health literacy, self-efficacy and side effects, to limited social support for PrEP use and PrEP-related stigma at the community level. PrEP programmes in South Africa are implementing many approaches to try and improve PrEP uptake and continuation in South Africa; however, there is a lack of evidence behind these strategies and to what extent these programme implementation strategies are effective for women at the highest risk.

Currently TB HIV Care is implementing large scale PrEP programmes for FSW and AGYW across four provinces (KwaZulu-Natal, Mpumalanga, Eastern Cape and North West Province) in South Africa. PrEP is provided by professional nurses at drop-in centres and mobile vans – implemented largely within communities. As such, TB HIV Care will lead the cluster randomized trial and data collection within the existing programme sites. TB HIV Care has extensive experience working with FSW and AGYW, as they have been providing HIV prevention services, including HIV testing and counseling, sexually transmitted infection screening and treatment, and condom provision to marginalized young women since 2012 through the mobile van health clinics and drop-in centre wellness clinics. PrEP service delivery for FSW across TB HIV Care supported sites in South Africa began in 2016, expanding in line with DOH priorities to AGYW in 2018 (mobile teams, community outreach, staff placement at DOH clinics). The TB HIV Care programme is funded through 2024 and had already initiated >20,000 women on PrEP in 2020. As the programme evolves, so do the interventions to support sustained PrEP uptake. The services for women are provided through both the FSW and AGYW programmes which have substantial areas of overlap. Programmatic data from TB HIV Care reinforce earlier results from South Africa that PrEP uptake among young women is relatively low, and PrEP use falls by nearly half at 1-month, continuing a steep decline until 7-months. Challenges in PrEP uptake and persistence are similar across sites. These data highlight the potential impact of this research to rigorously evaluate PrEP implementation strategies to initiate and maintain young women on PrEP during periods of heightened HIV risk as the programme continues to expand in coming years.

### **3. OBJECTIVES OF THE STUDY:**

Overall, the aim of this study is to evaluate implementation and effectiveness of a social media campaign and community engagement activites to promote PrEP uptake among women and to influence community norms around PrEP in South Africa. During a previous, largely completed phase of research within this grant we evaluated implementation and indications of effectiveness of ongoing PrEP uptake and retention strategies being promoted by TB HIV Care as part of their AGYW and FSW PrEP programmes. Based on these findings and in consultation with programme stakeholders, we have are proposing a pragmatic trial which will introduce adaptations to current services to work to further improve programme impact (Phase 2 of the grant research being submitted now).

The goal of the proposed study is thus to evaluate the relative effectiveness of modified PrEP implementation strategies on increasing uptake and sustained PrEP adherence among marginalized young women. This phase is focused on introducing modified and focused strategies to promote PrEP within the TB HIV Care HIV prevention programme. The effect of these modifications on sustained PrEP uptake and adherence will be tested using a short duration cluster randomized trial (CRT).

An important point of clarity is that the proposed CRT will not engage in PrEP provision to individuals. Rather, the CDC funded programme employs a large team to provide service delivery. The CRT merely is testing strategies that may amplify uptake and persistence among the community, leveraging the programme infrastructure to actually provide services as it is already doing. Embedding strategies within the programme ensures that the existing results come from real world contexts and focuses on implementation of support strategies rather than clinical care provision.

#### **4. STUDY DESIGN:**

This grant combines evaluation of ongoing PrEP programme implementation (previous work) with modified, programme informed implementation strategies for testing through two short-duration cluster randomized trials (CRTs). Specifically, this study protocol is focused on PrEP programme optimization through modifying the implementation strategies of ongoing programmatic activities by adjusting the delivery modalities and actors promoting PrEP within the community. The effect of these modifications on PrEP uptake (primary outcome) and continuation (secondary outcome) will be tested using an initial CRT. A second CRT focused primarily on PrEP continuation (retention) will be included in a separate, future protocol.

TB HIV Care is a South African non-profit organization that works directly with the Department of Health as the country's largest PrEP provider for AGYW and FSW. TB HIV Care has initiated over 33,000 women at high risk for HIV infection on PrEP, and has 13 active sites as of 2021. Of note, these are two PrEP programmes that are run by TB HIV Care (8 of the 13 active sites are part of the FSW programme and 5 of the 13 active sites are part of the AGYW programme). **The proposed study design leverages a cluster randomized trial design as some intervention components may not be feasibly randomized at the individual-level (e.g. PrEP peer ambassadors operating within venues/community locations, community mobilization and social media ads).** This trial is feasible given the short duration of the outcomes measured (PrEP uptake and 1- and 4-month PrEP persistence) and utilization of routine programme data for primary outcome ascertainment, and the testing is an adaptation of existing interventions. Based on the programme team's experience and PrEP barriers literature, this first CRT will focus on generating sustained PrEP demand, but also destigmatizing PrEP within young women's social environments (e.g. family, friends, partners). **CRT1 is described within this application.** The second CRT will likely optimize peer support mechanisms during the early days of PrEP use, but this will be refined in late 2022 based on the programme's input and a separate protocol will be submitted surrounding CRT2.

#### **PrEP Social Influence Campaign CRT:**

The CRT under current consideration will compare the existing standardized community engagement model (i.e. PrEP sensitization/promotion) to an enhanced PrEP social influence campaign using different delivery mechanisms. **The primary outcome will be the proportion of FSW/AGYW clients within the TB HIV Care PrEP programme who initiate PrEP among all eligible marginalized young women to whom it is offered.** Secondary outcomes will be differences in knowledge, attitudes and peer influence across arms (described in sections below)

and 1 and 4-month sustained PrEP use among PrEP initiators. The enhanced social media campaign will be implemented for 12-months while the PrEP champion and community mobilization interventions will be implemented for 6-months and will target young women, parents, teachers, peers, and partners. 5 TB HIV Care district sites within the four provinces will be randomized to each arm (10 districts randomized in total).

There will be two main study arms which will be randomized 1:1 at the district level across the 10 sites which span four provinces. **Arm 1** will receive PrEP sensitization per the ongoing programmatic Standard of Care. **Arm 2** will receive the standard of care through the programme per normal, as well as an enhanced social media intervention that will be targeted to the intervention districts. This is feasible because through social media platforms like Facebook, advertisements can be geographically targeted to specific areas. The primary outcome of PrEP uptake will be powered to assess the difference in PrEP initiations across the 10 sites, comparing PrEP uptake numbers in Arms 1 and 2. Additionally, a second layer of enhancement will be layered onto the intervention arms (Arm 2). Thus in addition to the social media campaign, wards from the five intervention districts will be randomly selected to implement: a) Nothing additional; b) Training and support for venue-based PrEP champions; c) PrEP community mobilization teams; d) Training and support for venue-based PrEP champions AND PrEP community mobilization teams. Details are further highlighted in Table 1 below:

Table 1: Intervention activities and CRT plan		
Arm	Name	Description
Arm 1*	Standard of care	Full-time peer educators employed by the programme to engage women, layer PrEP promotion across prevention programs, and implement “refer a friend” strategies, information, education and communication (IEC) materials, service user testimonials, risk reduction posters to increase young women’s perception of risk, working after hours/weekends to reach young women, working with school governing bodies, and door-to-door outreach.
Arm 2*	Enhanced social media campaign	PrEP social influence campaign, which will use online approaches to promote PrEP within communities in addition to the standard of care activities. Messaging crafted with community input will be geographically targeted to women, parents/mentors, and male partners on Facebook and/or Instagram (final platforms to be determined based on marketing research conducted by Community Health Trust who will contracted to manage the campaign), all with the intention to promote PrEP for women at high risk of HIV infection and change community norms and influence around PrEP. A combination of static imagery and brief videos will be used to engage these groups via social media platforms. High profile social influencers may be engaged as faces of the campaign, including for ads and video creation. A Facebook page will be created and maintained that can be accessed by anyone anywhere, but will only be advertised/promoted in the intervention districts.
Arm 2a**	Nothing additional	Wards in Arm 2a will not receive any additional strategies. They will still receive (as will all arms) the standard of care, as well as the enhanced social media campaign received by all wards in Arm 2.

Arm 2b**	PrEP champions	Within venues served by the FSW and AGYW programs, we will identify and train 1 venue-based PrEP champion per venue who will (a) have completed a 2 day group-based (cross-venue) health information training related to PrEP knowledge, with pre and post testing knowledge assessments to identify knowledge gaps; (b) receive supplies (e.g. a hat, pin and posters, flyers, IEC material) to wear to promote PrEP; (c) facilitate linkage between women interested in PrEP and the TB HIV Care PrEP programme; and (d) receive bi-weekly follow-up support from TB HIV Care to discuss challenges, progress and referrals. A partial day refresher training will be held at 3-months. PrEP champions will be either peers with experience taking PrEP, venue managers or local influencers (e.g. women running shops next to the mobile serving AGYW) that have repeated contact with the women the programme is intended to serve. The final selection of PrEP champions will be made in consultation with the Community Advisory Groups, venues and by the programme who works closely with each of the sites. The PrEP champions will receive a small airtime stipend (R150 per month) to follow-up and provide support to women engaging in PrEP.
Arm 2c**	PrEP community mobilization	A PrEP community mobilization team (2 peers, including one woman and one man) will be recruited within each ward to promote PrEP. The team will present information about PrEP and the PrEP programme at the ward councilors meeting, at Learning Support Agent meetings with parents/guardians, at local events/fairs, community meetings and through engaging men, women and parents across the community through informal conversations. Teams will be wearing branded material and will focus on presenting factual information and decreasing PrEP stigma, and will have received 3 days of training in HIV, PrEP, and health communication and persuasion to promote positive PrEP norms and attitudes within the community, with a 1-day refresher training at 3-months. Each team will focus on promoting PrEP within their own ward over the 6-month period.
Arm 2d**	PrEP champions + PrEP community mobilization	Wards in Arm 2d will receive both of the two additional strategies described above (2b & 2c).

\*10 districts randomized 1:1 across Arms 1 and 2.

\*\* Each of the wards (~216) across the 5 districts will be randomized to receive additional layered activities intended to change social norms around PrEP and amplify the social media campaign

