#### *B. Sample Size Considerations*

**Social influence campaign (CRT):** The primary outcome for this study will be PrEP uptake within the TB HIV Care programme. Each of the 10 cities in which TB HIV Care provides PrEP will be included as clusters. Assuming between 500 and 1000 PrEP-eligible women reached by the TB HIV Care PrEP programme per geographic region annually, we considered a coefficient of variation (CV) ranging from 0.25 to 0.4, and a minimum improvement in uptake of 10 percentage points (5% to 15%). With a conservative CV of 0.4, 5 clusters per arm will provide 87% power to detect this difference at an  $\alpha=0.05$  level of significance. For the second layer of randomization for enhanced social influence activities, a total of 216 wards (a smaller unit of subdivision used in South Africa to divide regions for political and administrative purposes) exist across the 5 intervention sites, which will be randomized across four sub-arms. There will be roughly 54 wards per sub-arm each with at least 10 PrEP-eligible women. Overall, arm 2 is hypothesized to have PrEP initiations of 15% where the least effective sub-arm [no additional enhancement] has an uptake rate of ~10% and the most effective sub-arm [2d which combines PrEP champions and PrEP community mobilization will have] will have an uptake rate of up to ~20%. Having at least 30 venues per sub-arm would provide 84% power, at a 5% level of significance, assuming a conservatively high CV of 0.4, to detect this difference. As this will be an exploratory investigation, the emphasis will be on the additional yield by the enhancements and thus no correction for the multi-arm hypothesis testing will be conducted.

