#### *C. Statistical Analysis Plan*

Results will be synthesized across the data sources and implementation outcomes, and utilized to assess the reach and effectiveness of social influence campaign strategies. Findings from the review of programme logs, social media metrics, and cross-sectional surveys will be reported. Costing data and ranges of intervention fidelity and penetration parameters will be used to inform programme activities. A comparison of the social influence campaign intervention vs standard of care at achieving PrEP uptake (primary), 1-month PrEP persistence (secondary) and 4-month PrEP persistence (secondary) will be key outcomes. Cluster level proportions of clients within the TB HIV Care PrEP programme who initiate PrEP will be compared between the main study arms using the unpaired t-test after a log-transformation if necessary. A secondary analysis will adjust for residual confounding by age and other individual characteristics through a two-stage logistic regression residuals approach. A similar approach will be used for the secondary outcomes and the comparison between sub-arms within the intervention main arm. Changes in PrEP knowledge, attitudes and social support across intervention and control areas over the two time periods (pre- and post-intervention) will be estimated using a difference in differences approach. Prevalence of PrEP knowledge, attitudes and social support across intervention and control areas over the two time periods (pre- and post-intervention) will be summarized by questions/item. Multivariate analysis will be conducted to generate patterns of responses by theme (e.g. perceptions of PrEP). Changes over time will be analysed using the difference in differences approach that uses suitable regression models (e.g. logistic, linear) to study the effect of time period and study arm, as well as their interaction, on the responses.

Analysis of data will be conducted using STATA Version 15.0.

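### Persistence is compared between arms only among women who start PrEP, a group the campaign is meant to change, and no pre-specified outcome tests sustained use among all eligible women offered it

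*Combined protocol and SAP*

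**What the plan says.** Section 3 (Objectives) gives the goal as "increasing uptake and sustained PrEP adherence among marginalized young women". It adds: "The effect of these modifications on sustained PrEP uptake and adherence will be tested using a short duration cluster randomized trial (CRT").

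Section 4 (PrEP Social Influence Campaign CRT) defines two kinds of programme outcome with different denominators. The primary outcome is the proportion of clients "who initiate PrEP among all eligible marginalized young women to whom it is offered". The secondary persistence outcomes are "and 1 and 4-month sustained PrEP use among PrEP initiators".

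Section 7.C (Statistical Analysis Plan) lists 1- and 4-month persistence among the key outcomes for the campaign versus standard of care. It compares cluster proportions for uptake with an unpaired t-test, adds a secondary analysis adjusted for age and other individual characteristics, and then says: "A similar approach will be used for the secondary outcomes and the comparison between sub-arms within the intervention main arm".

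Sections 7.D and 10.E mention persistence or continuation within the programme, but neither defines sustained use per eligible woman offered PrEP. The documents do not discuss selection into the group of starters.

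**The concern.** Randomisation makes the districts comparable in expectation. It does not make the women who start PrEP in one arm comparable with those who start in the other, because starting is a response to what was randomised. If the campaign works as intended, Arm 2 starters include women who would not have started under standard of care, and these women may be more or less likely to stay on PrEP.

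If they stop sooner, Arm 2 shows lower persistence even though no woman's persistence was harmed and more women are on PrEP at follow-up. If they are more committed, Arm 2 shows a persistence benefit that comes only from who started. A reader of the results could take either as an effect of the campaign on retention.

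The sub-arm comparisons have the same difficulty. It is sharper where PrEP champions are used, because Table 1 has them both link women to the programme and support women already taking PrEP. A real support effect and a change in who starts would be mixed in one number.

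**Working it through.** **1. The plan's own figure.** Section 7.B gives 87% power for uptake of 5% vs 15% with 5 clusters per arm and a CV of 0.4. It assumes 500 to 1000 eligible women per cluster. The usual unmatched cluster formula, two-sided 5%, is

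power = Φ( √{ (c−1)(p1−p0)² / [p0(1−p0)/m + p1(1−p1)/m + k²(p0²+p1²)] } − 1.96 ).

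With c = 5, k = 0.4 and m = 1000, the denominator is 0.0000475 + 0.0001275 + 0.0040 = 0.004175. Then √(0.04/0.004175) = 3.095 and Φ(1.135) = 87.2%. With m = 500 the result is 85.8%. The stated figure is reproduced, so 5% vs 15% is the right planning scenario to carry forward. The plan gives no power for persistence.

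**2. Share of induced starters.** If no woman starts only because she is in Arm 1, the share of Arm 2 starters who would not otherwise have started is (15−5)/15 = 67%. For sub-arms 2a and 2d, at the hypothesised 10% and 20%, it is (20−10)/20 = 50%.

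**3. Effect on the two measures.** Section 2 says that persistence roughly halves by 1 month, so take 50% for women who would start anyway, unchanged by the campaign. Let e be 1-month persistence in induced starters. The documents give no value for e, so it is an assumption shown over a range.

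- Arm 2 persistence among starters = (5×0.50 + 10×e)/15
- Arm 2 women on PrEP per 100 offered = 5×0.50 + 10×e
- Arm 1: 50% among starters, and 5×0.50 = 2.5 per 100 offered

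| e | Among starters, Arm 1 vs Arm 2 | Difference (points) | Per 100 offered, Arm 1 vs Arm 2 |
|---|---|---|---|
| 10% | 50% vs 23.3% | −26.7 | 2.5 vs 3.5 |
| 30% | 50% vs 36.7% | −13.3 | 2.5 vs 5.5 |
| 50% | 50% vs 50% | 0 | 2.5 vs 7.5 |
| 70% | 50% vs 63.3% | +13.3 | 2.5 vs 9.5 |

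No woman's persistence is altered by the campaign in any row. Arm 2 persistence among starters could fall to 2.5/15 = 16.7% before sustained use per woman offered was no better than in Arm 1.

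**4. A smaller uptake effect.** If uptake were 5% vs 10% (assumption) and e = 30%, the induced share is 5/10 = 50%. Persistence among starters is (2.5+1.5)/10 = 40% against 50%, and women on PrEP per 100 offered are 2.5 vs 4.0. The distortion shrinks but keeps its direction.

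**5. How the two tests behave in the e = 30% row.** The formula in step 1 was applied to each outcome, using "a coefficient of variation (CV) ranging from 0.25 to 0.4". The plan states that range for uptake, and its use for persistence is an assumption. With 500 to 1000 women offered per cluster, the starter-only estimate is lower in Arm 2 with probability about 86% to 96%, and significantly so about 16% to 33% of the time. The per-offered comparison has about 60% to 93% power in favour of Arm 2. These figures apply only if e is 30%. They do not say how likely that is.

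**The case against.** *The information is already there.* Sustained use per woman offered is uptake times persistence among starters, and both are planned per cluster from programme data: 15% × 36.7% = 5.5% and 5% × 50% = 2.5%. This stands. A reader might infer that the trial cannot say whether the campaign raises sustained use. The documents do not support that. What is missing is a pre-specified outcome with its own test and interval.

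*Adjustment is planned.* Section 7.C adjusts for age and other individual characteristics and extends a similar approach to the secondary outcomes. That is a partial safeguard. Age is the only characteristic named, and nothing indicates that the registers measure motivation to stay on PrEP.

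*Persistence is not the focus.* Section 3 puts uptake and community norms first, and Section 4 makes continuation secondary and leaves a retention-focused trial to a separate protocol. The goal can also be read as two questions, starting and then staying on, for which a starter denominator is a conventional programme measure. This limits the weight of the point. It does not remove it, because Section 3 says this trial will test sustained uptake and Section 7.C lists persistence among the key outcomes.

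*The reversal is hypothetical.* This is correct. A reader might infer that the persistence result will point the wrong way. That needs induced starters to persist less than the others, and the documents say nothing on this. At equal persistence there is no distortion.

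*The offered denominator is not clean either.* This also stands. Women enter the data by using a programme service, and the campaign may change who is reached and offered PrEP. The primary outcome shares this weakness.

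**Conclusion.** The point holds in a limited form. The only specified persistence comparison conditions on a post-randomisation event that the campaign is designed to change, and no specified outcome tests sustained use on the primary outcome's denominator. At the planned effect about two thirds of Arm 2 starters would be campaign-induced. A 20-point difference in persistence between induced and other starters, in either direction, would move the starter-only contrast by 13.3 points with no effect on any woman's persistence.

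This rests on three assumptions: the full 5% to 15% effect is reached, no woman starts only under standard of care, and 1-month persistence is 50% in women who would start anyway. The direction of the distortion rests on a quantity the documents do not give. The primary uptake analysis is unaffected by this point. The change should be made before the analysis, because without it one stated goal has no direct pre-specified test.

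**What to change.** In Section 4 (outcomes) and Section 7.C (analysis):

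- Add two secondary outcomes: the cluster proportion of eligible women offered PrEP who initiate and are still on PrEP at 1 month, and the same at 4 months. Analyse them with the same cluster-level test as uptake, between arms and between sub-arms.
- Restrict each denominator to women offered PrEP early enough to complete that follow-up within the data period, or extend the register extraction. Section 6 describes follow-ups completed within the 12-month period, so women offered PrEP late would otherwise be counted as not sustained.
- Keep persistence among starters alongside, labelled as not a randomised comparison.
- Report numbers reached and offered PrEP by arm and sub-arm, because the campaign may also change who is offered it.

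The cost is protocol and analysis-plan wording and two more proportions per cluster, from programme data already planned for use. Numerators are small: at 2.5% of 500 to 1000 women, a control district would have about 12 to 25 women on PrEP at 1 month. The starter-only measure has the same numerator over only 25 to 50 starters (5% of 500 to 1000). Without extended extraction, and if offers are spread evenly over the year (assumption), the denominator loses about 1/12 = 8% at 1 month and 4/12 = 33% at 4 months. Extending the extraction avoids that loss but delays the final data.
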